Aim 2: To evaluate the potential of wearable assistance at the ankle, knee, and/or hip joints to increase walking performance in older individuals.

Lay Summary:

Project Narrative for Prospective Research

Many older individuals have impaired walking ability that limit quality of life and lead to long-term health consequences. Reduced physical activity from age-related decline in gait dysfunction can lead to a downward spiral that results in a deterioration of walking ability with age, ultimately leading to a loss of ambulation in a large portion of the affected population.

The goal of this research protocol is to improve mobility in older individuals through advances in wearable assistive devices by focusing on two specific aims. The first aim is to study if targeted ankle resistance gait training improves walking performance in older individuals. The second aim is to evaluate the potential of wearable assistance at the ankle, knee, and/or hip joints to increase walking performance in older individuals.

Resources:

This study will take place in the Biomechatronics Lab led by PI Assoc. [name]. Post-docs, graduate student researchers and undergraduate student researchers will be assisting with data collection and processing.

Population & Recruitment

- Maximum number of participants to be enrolled in the study: 30
- Please check all the categories of participants that will be included in the research:

 Children (1-17 yrs old)- Complete Appendix A	 Adults
 Prisoners- Complete Appendix C	 Refugees
 Native Americans - See the Tribal Consultation Policy	 NAU Staff/Faculty
 Pregnant Woman/ Neonates – Complete Appendix B	 NAU Students
 Cognitively Impaired Subjects	 Other- Explain Below

- What are the inclusion and exclusion criteria for study participation?

Subject population will include:

- 30 older individuals with age-related walking deficits. We will recruit 33 individuals anticipating a 10% withdrawal rate to obtain the target sample size.

Inclusion criteria:

- Age between 65 and 85 years old, inclusive.
- Must be able to understand and follow simple directions based on parent report and clinical observation during the history and physical examination.

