- Able to provide verbal assent, if appropriate. If the participant is non-verbal, parental interpretation of gesticulation for assent will be used.
- The ability to read and understand English.
- Able to walk at least 30 feet with or without a walking aid
- Able to safely fit into a device configuration and tolerate assistance without knee

Project Narrative for Prospective Research

hyperextension while walking

Exclusion criteria:

- Any neurological, musculoskeletal or cardiorespiratory injury, health condition (including pregnancy), or diagnosis that would affect the ability to walk as directed for short periods of time. Note: For elderly participants, a history of joint replacement or joint degeneration that does not impair their ability to walk safely is allowable.
- Participant or parent report that the prospective participant's physician has recommended that they not engage in moderate intensity walking exercise.

Note: No exclusions will be made on the basis of race, gender or ethnic background and efforts will be made to recruit underrepresented minorities.

- Indicate age range, gender and ethnicity of your research population:
There will be no restriction on sex, gender, ethnicity, or race.
Age between 65-85 years old.
- Will there be any individuals working on the research project (consenting, collecting data, analyzing identifiable data) who are not affiliated with NAU? No Yes- Please complete **Appendix E: Multi-site Research** for each unique site if the site will not obtain their own IRB approval.
- Will any documents be translated into another language? No Yes- Please explain below
Explain: Click or tap here to enter text.
- Please select the methods that will be used to recruit individuals. **Provide copies of documents, as applicable.**

 Email	 Social Media
 Flyers	 Online Advertisements
 TV, Radio, Print	 Phone Calls
 In Person Presentations	 Screening of the Electronic Medical Record (EMR)
 Face to Face	 SONA
	 Other- Please explain below

Explain: We will use an email, phone, and face to face script for participant recruiting

- When will recruitment occur? Please provide time frame with dates if applicable: 1/1/2024-1/1/2027

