- 3) Walking at a mild incline/decline (0°-15°) on the treadmill
- 4) "Walking" on a steppmill machine
- 5) Walking on stairs
- 6) Balance on a treadmill
- 7) All terrain walking over ground
- 8) Mobility analysis
- 9) At-home walking and/or running, and usability testing

Orthosis Conditions:

- 1) *Walking or running without assistance/resistance:* We will obtain the normal/representative walking pattern of each participant. This condition will be used to compare the effectiveness of the assistive conditions.
- 2) *Walking with basic powered orthosis assistance/resistance:* We will provide on/off assistance/resistance during walking, depending on the individual's specific gait deficits.
- 3) *Walking with adaptable powered orthosis assistance/resistance:* We will provide assistance/resistance that changes magnitude based on measures of gait performance.

Project Narrative for Prospective Research

- 4) *Walking with powered assistance/resistance and biofeedback:* We will combine assistance with real-time feedback of walking performance. Individually tuned performance measures will be identified for each participant, and used to identify walking goals. Participants will be instructed to try to meet and maintain their goals.
- 5) *Walking with passive (unpowered) orthosis assistance:* We will evaluate the ankle neutral angle and AFO stiffness that are more beneficial for each participant.

In Laboratory Mobility analysis:

To assess mobility, participants will undergo the following tests, with or without a powered orthosis, under direct supervision by a research team member, who will be available to spot for safety (heart rate and metabolic cost may be collected):

- 1) Timed up and go: participants will walk as quickly as possible in a safe and controlled manner to a cone 3 meters away, turn around, walk back to the chair and sit down; 3 – 6 trials will be collected.
- 2) 6 minute walk test: participants will walk as quickly as possible in a safe and controlled manner for 6 minutes to test walking endurance; 1 – 3 trials will be collected.

All terrain walking over ground:

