Participants will be monitored and accompanied at all times by the trained safety advocate and study staff during indoor or outdoor all terrain walking or running trials that may take place on or off campus. Trials will include ambulation with and without wearable assistance. On-campus locations will include the Engineering, Business, and Learning resource Center buildings, the north and south quads, and campus walkways and urban trails. Off-campus locations will include Buffalo Park and surrounding Elden trails.

Data Collection: Experimental data collection will include motion capture (movement and force gait analysis), measurement of muscle activity (electromyography, EMG), measurement of reflexes (H-Reflex), measurement of muscle architecture (Ultrasound), measurement of oxygen consumption/cO₂ production (metabolic rate), and brain activity (electroencephalography, EEG).

Physical activity questionnaire: We will ask questions to understand the physical activity levels of older adults.

Description of laboratory visits for ankle resistance training:

Pre-visit phone call: Optional phone call prior to first in-person visit (but after consent) to collect relevant medical history and physical activity questionnaire.

Visit 1: Participants will undergo consent (if not done over the phone), history/physical/activity questionnaire, and orthotic device fitting. Following device fitting, the participants will undergo a pre-assessment baseline gait and mobility analysis, and then practice walking with powered resistance. The expected duration is 3-4 hours.

Project Narrative for Prospective Research

Visits 2 through 13: On each visit, participants will complete 20-30 minutes of ankle resistance training. This will involve walking on a treadmill with stance phase ankle resistance and biofeedback.

Final visit: On the post-assessment visit participants will complete a follow-up gait and mobility analysis. The expected duration is 2 – 3 hours.

Timeline: The participants will be asked to complete 1-4 visits per week for 3-12 weeks. To accommodate illness, travel, and scheduling conflicts, the maximum time that a participant can be enrolled in the study is 16 weeks.

Description of laboratory visits for walking with assistance:

Pre-visit phone call: Optional phone call prior to first in-person visit (but after consent) to collect relevant medical history.

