Visit 1: Participants will undergo consent (if not done over the phone), history/physical/activity questionnaire, and orthotic device fitting. Following device fitting, the participants will undergo a pre-assessment baseline gait and mobility analysis with and/or without assistance. The expected duration is 3-4 hours.

Visits 2 through a maximum of 17: On each visit, participants will complete 20-40 minutes of walking with powered or passive assistance at the ankle, knee, or hip joints.

Final visit: On the post-assessment visit participants will complete a follow-up gait and mobility analysis with and/or without assistance. The expected duration is 2 – 3 hours.

Timeline: The participants will be asked to complete 1-4 visits per week for 3-12 weeks. To accommodate illness, travel, and scheduling conflicts, the maximum time that a participant can be enrolled in the study is 16 weeks.

Recruitment: We will recruit people from our network of individuals/families of a child with CP and from PT clinics and hospitals across the state of Arizona.

Management of Project Personnel: [name] will be responsible for managing project research personnel (graduate students, staff, etc.), including their CITI Training.

3. Please state the estimated time commitment for subject participation: The estimated time commitment to complete the assigned study tasks is 1-18 sessions, each lasting up to 1-4 hours.
4. Does this project involve investigating a Drug, Device or Biologic? No Yes- Complete **Appendix F: Drugs and Devices**
5. Is this project a Clinical Trial? No Yes See [clinical trial guidance](#)

Project Narrative for Prospective Research

*A research study in which one or more human subjects are prospectively assigned to one or more interventions (which may include placebo or other control) to evaluate the effects of the interventions on biomedical or behavioral health-related outcomes.

Compensation & Costs

(See [Compensation of Subjects](#) Guidance)

1. Provide the amount of compensation (monetary and/or non-monetary) subjects may receive:

Subjects will receive monetary compensation for their participation in the study.

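### Experimental condition 9 allows running at home for 65-85-year-olds with walking deficits, where no written staff-presence or physical safeguard clearly applies and no stated aim needs it

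*Protocol*

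**What the plan says.** Under Data Collection Procedures, item 2, the protocol lists nine experimental conditions. The ninth is "At-home walking and/or running, and usability testing". Running is not confined to that item. The lead-in to the list puts both walking and running in scope, Orthosis Condition 1 covers walking or running with no assistance or resistance, and the all-terrain section includes running trials.

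The subject population is "30 older individuals with age-related walking deficits", aged 65 to 85. Four eligibility criteria bear on mobility or device tolerance:

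- Inclusion: "Able to walk at least 30 feet with or without a walking aid".
- Inclusion: safe device fit, with no knee hyperextension while walking.
- Exclusion: an injury, condition or diagnosis that "would affect the ability to walk as directed for short periods of time".
- Exclusion: a report that the person's physician has "recommended that they not engage in moderate intensity walking exercise".

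Staff also assess each person at Visit 1, with a history, a physical, an activity questionnaire and a device fitting. In the resistance part, "the participants will undergo a pre-assessment baseline gait and mobility analysis, and then practice walking with powered resistance". In the assistance part, "the participants will undergo a pre-assessment baseline gait and mobility analysis with and/or without assistance".

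The section on all-terrain walking says that participants will be "accompanied at all times by the trained safety advocate and study staff during indoor or outdoor all terrain walking or running trials". The sites it names are campus buildings, quads, walkways and trails, and an off-campus park with nearby trails.

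**The concern.** The protocol requires staff to be present at all times when participants run on all-terrain routes. For running at home it states no equivalent. A participant could meet the walking floor by covering about 9 m with an aid, and the listed conditions would then allow running at home. The Benefits & Risks section itself names injury from a fall during running as a risk.

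What is at stake is participant safety, not inference. If home running served an aim, the risk would need to be weighed against what the study learns from it. If it serves none, the permission can go at almost no cost.

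**Working it through.** This is a check of text against text. The plan gives no figure on this point, so there is none to reproduce.

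**Step 1. Screening.** Of the four mobility or device-tolerance criteria, four concern walking and none concerns running. The distance floor is 30 ft × 0.3048 = 9.14 m, with an aid allowed. The Visit 1 assessments could tell staff who is fit to run, but no criterion directs them to that question.

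**Step 2. Safeguards.**

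| Safeguard | Protocol section | Written for | Names running? | Clearly reaches a home run? |
|---|---|---|---|---|
| Spotting by staff | In Laboratory Mobility analysis | Timed up and go, six-minute walk | No | No |
| Accompaniment at all times | All terrain walking over ground | All-terrain trials, on or off campus | Yes | Not clearly |
| Overhead tether | Benefits & Risks, item 4 | Treadmill walking, if unstable | No | No |
| Automatic deactivation | Benefits & Risks, item 4 | Powered devices, any place | No | Yes, if a powered device is worn |

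Of the three staff-presence or physical-support safeguards, one names running and none is written for the home. The accompaniment rule is the closest. Its references to indoor and off-campus trials could be stretched to a home. However, it sits under the all-terrain heading, its named sites are campus, park and trails, and all-terrain walking (item 7) is listed separately from at-home activity (item 9).

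Automatic deactivation has no location limit and is a real safeguard. It does nothing when a passive device or no device is worn. The only orthosis condition that names running is the one without assistance or resistance, although the lead-in to the experimental conditions does not rule out powered running.

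**Step 3. Use made of home running.**

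- Aims: 0 of 2 name running. Both concern walking performance.
- Visit schedules: resistance training has 1 + 12 + 1 = 14 visits (Visit 1, Visits 2 to 13, final visit). Assistance has up to 1 + 16 + 1 = 18 (Visit 1, Visits 2 to 17, final visit). Both are headed as laboratory visits, and neither contains a home session or a run.
- SAP outcomes: 0 of 5 concern running. They are plantarflexor strength, habitual and fastest walking speed, six-minute walk distance and cost of transport in treadmill walking. This is weak evidence taken alone, because stairs, the stepping machine and balance are also listed conditions with no SAP outcome.

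**Step 4. Number exposed.** It is not stated. The range is 0 to 30 by the enrolment cap, or 0 to 33 by the recruitment figure.

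**The case against.** The strongest reply is that nobody is scheduled to run at home. Item 9 offers running as an option, the visit schedules contain no home session, and the exposure may be nil. That stands, and it keeps the point small. It also makes the permission easy to give up.

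A second reply is that screening is fuller than the criteria suggest. Visit 1 includes a physical, an activity questionnaire and a gait and mobility analysis, and conditions that affect directed walking are excluded. This stands in part: staff would know a good deal about each person, but the protocol does not make any of it a test of fitness to run.

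A third reply is that the overarching goal is mobility in general, and that item 9 pairs running with usability testing. Home running could serve that goal loosely. It still serves neither specific aim and no listed analysis.

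A reader might infer more than the documents support in four ways:

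- **That home running would be unsupervised.** The protocol does not say so. It leaves staff presence at home open.
- **That running appears only in item 9.** It is the only one of the nine listed items to name running, but the lead-in, Orthosis Condition 1 and the all-terrain section all include it.
- **That removing it from item 9 closes the eligibility gap.** The walking-only criteria apply to all running in the study, so the deletion removes only the setting with the least written protection.
- **That the lack of injury provisions is special to home running.** The Compensation & Costs section proposes none for any activity, so this is a separate matter and adds nothing here.

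**Conclusion.** The point holds as a minor participant-safety improvement. Item 9 permits running at home, in people aged 65 to 85 with walking deficits who are screened only on walking, and none of the three staff-presence or physical-support safeguards is clearly written for that setting. Home running serves neither stated aim, appears in neither visit schedule and feeds no SAP outcome.

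Its size is bounded by 0 to 30 participants (33 on the recruitment figure), and zero is possible. The conclusion rests on two readings: that the all-terrain accompaniment rule does not extend to the home, and that no home procedure exists outside the documents supplied. If staff attendance at home was always intended, the gap is one of wording. At-home walking and usability testing are not in question, and no estimate, test or trial conclusion is affected.

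**What to change.** Strike the words *and/or running* from item 9. Leave at-home walking, usability testing and accompanied all-terrain running unchanged.

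The cost is a short amendment and the loss of optional usability information on home running. Recruitment is planned to 1/1/2027, so the change could still apply to people enrolled after it.

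Keeping home running would instead mean a supervised laboratory run first, and extending the accompaniment rule to the home. That adds a procedure and staff time for each person who would run at home. For an activity that no aim asks for, the deletion is the better choice.

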**Principal Investigator**

**Ankle assistance and resistance in older adults**

**NCT06284525**

**1/15/2025**

## Statistical Analysis Plan

Functional outcomes of interest were (1) plantarflexor muscle strength, (2) habitual walking speed, (3) fastest walking speed, (4) six-minute walk test distance, and (5) the cost of transport (COT). For the six minute walk test, participants walked back-and-forth between the two cones spaced 15-meters apart while an investigator followed behind them with a distance measuring wheel (ML1212, Komelon, Waukesha, WI). Before beginning, the task was described to the participants, and they were told 'Let's see how far you can get in six minutes'. This test was performed one time to avoid participant fatigue, with the final distance, in meters, recorded as the outcome measure of interest.

To calculate the COT, we first calculated the metabolic power of the standing baseline and walking periods using Brockway's standard equation. Net metabolic power was then calculated by subtracting the standing baseline's metabolic power from the average metabolic power from the last two-minutes of treadmill walking and normalizing by participant body mass. Finally, cost of transport was determined by normalizing net metabolic power by the participant's treadmill walking speed.

Following the warm-up period, individuals performed maximum voluntary isometric contractions of the ankle plantarflexors while lying in a supine position by pressed their foot into a handheld dynamometer (microFET2, Hoggan Scientific, Salt Lake City, UT) that recorded the peak force, in newtons. While the individual was lying supine, a member of the research team held their knee to prevent flexion upon contraction of the plantarflexors. The test was performed once as a practice to familiarize the participant with the task and ensure no discomfort, followed by three bouts for each leg with adequate rest (determined by the user) between each bout. The average force across both legs was calculated and normalized by participant body mass.

### Statistical Analyses

All statistical tests were performed in SPSS (IBM, Armonk, NY). Two-tailed paired t-tests with a fixed significance level of  $\alpha = 0.05$  were used to compare strength, functional mobility, and energetic outcomes between the pre- and post-assessment visits. Prior to conducting the test, the assumptions of the test, namely normality and presence of outliers in the differences between assessments, were checked via Shapiro-Wilk tests and by plotting the data against a box plot with interquartile ranges. In instances where violations of the assumptions occurred, Wilcoxon signed-rank tests were utilized to assess the data.

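### Does letting a normality and box-plot check choose between the paired t-test and the Wilcoxon test, with no stated outlier fence, undermine the five pre/post comparisons?

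*SAP*

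**What the plan says.** The SAP's Statistical Analyses section sets "Two-tailed paired t-tests with a fixed significance level of" 0.05, and these "were used to compare strength, functional mobility, and energetic outcomes between the pre- and post-assessment visits". The assumptions to be checked first are listed as "namely normality and presence of outliers in the differences between assessments", and they "were checked via Shapiro-Wilk tests and by plotting the data against a box plot with interquartile ranges". The fallback is one sentence: "In instances where violations of the assumptions occurred, Wilcoxon signed-rank tests were utilized to assess the data".

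The opening of the SAP lists five outcomes, beginning "Functional outcomes of interest were (1) plantarflexor muscle strength, (2) habitual walking speed, (3) fastest walking speed" and ending with six-minute walk distance and cost of transport. None is named as primary.

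The SAP does not give a multiplier for the interquartile range, a cut-off for Shapiro-Wilk, or a rule for when the two checks disagree. It does not plan to report the test that was not chosen. The protocol has no statistical section that fills these gaps. It does give a study size under Population & Recruitment: "30 older individuals with age-related walking deficits", with 33 recruited to allow for withdrawal. That figure covers both aims, so the number of pairs behind each test is not stated.

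**The concern.** Three features look wrong together. The test is selected from the very differences it then tests. An outlier alone counts as a violation. The fence that defines an outlier is left open. The natural reading is that the choice is made outcome by outcome, so the five results could be divided between two tests.

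The paired t-test concerns the mean change, and the signed-rank test concerns the centre of symmetry (the pseudomedian, estimated by Hodges-Lehmann). If chance decides which is used, a reader cannot say in advance what a given p-value refers to. Two careful analysts could report different tests for the same outcome. Data-driven selection can also push the type I error above its nominal level. If these effects were large, the nominal 5% and the meaning of each result would both be in doubt.

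**Working it through.** **Inputs from the documents.** Two-sided level 0.05; default paired t-test; switch to Wilcoxon on non-normality or an outlier; five outcomes; target 30, recruited 33.

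**The one derived design figure.** 30 × 1.10 = 33, as stated. Dividing instead gives 30 / 0.90 = 33.3, or 34. One participant makes no difference here. The figure only sets the upper end of the sample sizes tried.

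**Assumptions, because the documents are silent.** Pairs per analysis from 10 to 33; Shapiro-Wilk cut-off 0.05; fence at 1.5 or 3 times the interquartile range (IQR), using Tukey hinges. The rule coded is: Wilcoxon if Shapiro-Wilk p < 0.05 or any point lies beyond the fence, otherwise the paired t-test.

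**Step 1: exactly normal differences, no effect** (20,000 simulated data sets per row; simulation standard error √(0.05 × 0.95 / 20,000) ≈ 0.0015 at 5%).

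| Pairs | Switch, 1.5 IQR | Switch, 3 IQR | t-test error | Rule error, 1.5 IQR |
|---|---|---|---|---|
| 10 | 22% | 7% | 5.3% | 5.5% |
| 15 | 30% | 6% | 5.0% | 5.3% |
| 20 | 25% | 6% | 4.7% | 5.1% |
| 30 | 31% | 5% | 5.0% | 5.5% |
| 33 | 37% | 6% | 5.0% | 5.4% |

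At 30 pairs the choice between the two fences changes the test used in 26% of data sets. If the five outcomes were independent, the chance that at least one switches is 1 − (1 − 0.3099)^5 = 0.84 with the narrow fence and 1 − (1 − 0.0534)^5 = 0.24 with the wide one.

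**Step 2: what a switch costs on normal data.** For a symmetric distribution the mean and the pseudomedian are the same number, so a chance switch leaves the target where it was. At 30 pairs the t-test and Wilcoxon disagree on significance in 1.7% of null data sets. The rule departs from the t-test only when it has also switched, so it gives the same decision in about 99%. At an assumed standardized change of 0.53, power is 80.6% for the rule and 80.2% for the t-test.

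**Step 3: skewed differences with zero mean, 30 pairs.** For a centred gamma, skewness = 2/√shape, so shape 4 gives 1 and shape 1 (exponential) gives 2.

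| Skewness | Switch, 1.5 IQR | t-test | Wilcoxon alone | Rule, 1.5 IQR | Rule, 3 IQR |
|---|---|---|---|---|---|
| 1 | 60.5% | 5.91% | 7.90% | 8.13% | 7.87% |
| 2 | 97.5% | 7.05% | 16.34% | 16.37% | 16.36% |

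The rule tracks Wilcoxon closely, so the excess over the t-test comes from the change of target and not from the act of selecting. The unstated fence moves the rejection rate by 8.13 − 7.87 = 0.26 points in the first row and 0.01 in the second.

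If pre and post values have the same distribution and are exchangeable, their differences are symmetric even when the raw values are skewed. With exponential pre and post values (12,000 data sets) the rule rejects in 5.3% and the t-test in 4.8%.

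**Step 4: would a fixed t-test be better?**
- *Error under strong skew (skewness 2), t-test against rule, 12,000 data sets:* 8.6% against 11.1% at 15 pairs; 10.3% against 9.7% at 10 pairs. With few pairs the fixed t-test gains nothing.
- *Power under symmetric heavy tails, t-test against rule, 8,000 data sets:* at 30 pairs and a shift of 0.45 SD, 69% against 78% (Laplace) and 75% against 87% (t with 3 degrees of freedom). At 15 pairs and a shift of 0.6 SD, 62% against 67% and 71% against 78%.

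The fixed test therefore gives up 78 − 69 = 9 to 87 − 75 = 12 points of power at 30 pairs in the setting that the SAP's outlier check is meant to catch.

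**The case for a change.** The best case for a change is that it costs only wording and some extra output. The SAP could keep its own default, the paired t-test with a confidence interval, for all five outcomes and add Wilcoxon with a Hodges-Lehmann estimate beside each. That would settle what every p-value refers to and stop an unstated fence from deciding anything. With clear skew and mean change as the quantity of interest, 16% rejection against 7% at 30 pairs is not trivial.

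Much of this stands as description. The fence and cut-off are missing, the selection uses the tested data, and under marked skew a Wilcoxon p-value should not be read as a test of the mean.

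It does not stand as a case for correction. The high switching rates under pure chance arise with normal differences, where the two tests share a target. The large gap in rejection arises under strong skew, where nearly every sample would switch whichever fence is used. The two do not add up to different quantities being tested by chance. Moderate skew lies between: the fence can change the test there (in 16% of data sets at skewness 1), but it hardly moves the error rate. A split between tests also spoils no planned comparison, because the five outcomes are in different units and the SAP neither pools nor compares them.

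Timing is a further limit. The SAP, dated 1/15/2025, describes the tests in the past tense, so naming one test in advance may no longer be possible. The documents do not settle this, since the protocol's recruitment period runs to 1/1/2027.

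**Conclusion.** The plan holds as written. The missing fence and cut-off are a gap that an analyst fills with a conventional value and makes visible by naming the test used for each outcome. Under normal or other symmetric differences the two-step rule adds about half a percentage point or less to the type I error and almost never changes a decision. Under skew the two tests answer different questions, but that follows from preferring a rank test for such data, which is a legitimate choice, and the unstated fence has almost no bearing on it. Replacing the rule with a fixed t-test exchanges one cost for another: closer control for the mean under strong skew at 15 to 30 pairs, no gain at 10, and roughly 9 to 12 points less power at 30 pairs when tails are heavy and symmetric.

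These figures rest on an assumed Shapiro-Wilk cut-off of 0.05, fences of 1.5 or 3 times the IQR, 10 to 33 pairs, and the distributions named above. Other quartile definitions shift the switching rates (26 to 35% at 30 pairs with the narrow fence). The one caution for a reader is to see which test produced each p-value and, where it was Wilcoxon, not to read it as evidence about the mean.
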